### 2.2.1. Primary Safety Estimands

The primary safety estimands for the primary objective will follow the treatment policy strategy from the EMA ICH E9 (R1) addendum^1 and estimate the safety percentages regardless of the occurrence of intercurrent event(s) or rescue medication use. The analyses will be based on the actual vaccine received.

Reactogenicity estimands after vaccination include the following attributes:

- Treatment: One of the dose/formulation levels defined as GBS6 (20 µg) and Tdap (GBS6+Tdap), GBS6 (20 µg) and placebo (GBS6+placebo), and Tdap and placebo (placebo+Tdap) (hereafter referred to as vaccine groups).
- Population: Healthy nonpregnant women 18 through 49 years old, inclusive, as defined by the study inclusion and exclusion criteria.
- Variable: Presence/absence and grade of any prespecified local reactions and systemic events within 7 days after vaccination.
- Intercurrent event(s): All collected data after the intercurrent event will be included; missing data will not be imputed.
- Population-level summary: Proportion of participants reporting prespecified local reactions and systemic events in each vaccine group.

AE, MAE, and SAE estimands after vaccination include the following attributes:

- Treatment: One of the dose/formulation levels defined as GBS6 (20 µg) and Tdap (GBS6+Tdap), GBS6 (20 µg) and placebo (GBS6+placebo), and Tdap and placebo (placebo+Tdap).
- Population: Healthy nonpregnant women 18 through 49 years old, inclusive, as defined by the study inclusion and exclusion criteria.
- Variables: Presence of AEs from the day of vaccination through 1 month after vaccination and presence of MAEs and SAEs from the day of vaccination through 6 months after vaccination.
- Intercurrent event(s): All collected data after the intercurrent event will be included; missing AE dates and missing AE severity will be handled according to Pfizer safety rules.
- Population-level summary: Proportion of participants reporting AEs, MAEs, and SAEs in each vaccine group.

## 2.2.2. Primary Immunogenicity Estimands

The primary immunogenicity estimands will use the hypothetical strategy to estimate the immune response when the intercurrent event would not occur. In other words, the immune response is estimated in the hypothetical setting where participants follow the study schedule and protocol requirements as directed.

Estimands for endpoints of anti-tetanus toxoid and anti-diphtheria toxoid antibodies include the following attributes:

- Treatment: One of the dose/formulation levels defined as GBS6 (20 µg) and Tdap (GBS6+Tdap) and Tdap and placebo (placebo+Tdap).
- Population: Healthy nonpregnant women 18 through 49 years old, inclusive, as defined by the study inclusion and exclusion criteria.
- Variable: Presence of anti-tetanus toxoid and anti-diphtheria toxoid antibody concentrations  $\geq 0.1$  IU/mL at 1 month after vaccination.
- Intercurrent event(s): The following intercurrent events could impact the interpretation or the measurement of the immune response:
  - The participant did not receive the study intervention as randomized.
  - The participant did not meet the study inclusion/exclusion criteria.
  - Major protocol violation – a protocol violation that, in the opinion of the sponsor's study medical monitor, would materially affect assessment of immunogenicity.
  - Blood was taken outside the window (<27 days or >45 days after vaccination).

The clinical question of interest is based on whether the immune response elicited from Tdap via coadministration with GBS6, without any influence from any other immune-modifying drugs or vaccines, measured in a homogeneous time point, is noninferior to that of Tdap administered alone (ie, without GBS6). Therefore, all data after intercurrent events, if applicable and collected, will be excluded. Major protocol violations will be determined by clinical review.

- Population-level summary: The differences and 2-sided 95% CI in proportions of participants with anti-tetanus toxoid and anti-diphtheria antibody concentrations  $\geq 0.1$  IU/mL at 1 month after vaccination between the GBS6+Tdap group and the placebo+Tdap group.

Estimands for endpoints of anti-pertussis component (pertussis toxin, FHA, and PRN) antibodies include the following attributes:

- Treatment: One of the dose/formulation levels defined as GBS6 (20 µg) and Tdap (GBS6+Tdap) and Tdap and placebo (placebo+Tdap).
- Population: Healthy nonpregnant women 18 through 49 years old, inclusive, as defined by the study inclusion and exclusion criteria.
- Variable: Anti-pertussis toxoid, anti-FHA, and anti-PRN antibody concentrations at 1 month after vaccination.
- Intercurrent event(s): The following intercurrent events could impact the interpretation or the measurement of the immune response:
  - The participant did not receive the study intervention as randomized.
  - The participant did not meet the study inclusion/exclusion criteria.
  - Major protocol violation – a protocol violation that, in the opinion of the sponsor's study medical monitor, would materially affect assessment of immunogenicity.
  - Blood was taken outside the window (<27 days or >45 days after vaccination).

The clinical question of interest is based on whether the immune response elicited from Tdap via coadministration with GBS6, without any influence from any other immune-modifying drugs or vaccines, measured in a homogeneous time point, is noninferior to that of Tdap administered alone (ie, without GBS6). Therefore, all data after intercurrent events, if applicable and collected, will be excluded. Major protocol violations will be determined by clinical review.

- Population-level summary: The GMRs and 2-sided 95% CI estimated by the GMR of antipertussis, anti-FHA, and anti-PRN antibodies measured at 1 month after vaccination from the GBS6+Tdap group to the placebo+Tdap group.

Estimands for endpoints of GBS CPS serotype-specific IgG antibody concentration include the following attributes:

- Treatment: One of the dose/formulation levels defined as GBS6 (20 µg) and Tdap (GBS6+Tdap) and GBS6 (20 µg) and placebo (GBS6+placebo).
- Population: Healthy nonpregnant women 18 through 49 years old, inclusive, as defined by the study inclusion and exclusion criteria.

- Variable: GBS CPS serotype-specific IgG concentrations at 1 month after vaccination.
- Intercurrent event(s): The following intercurrent events could impact the interpretation or the measurement of the immune response:
  - The participant did not receive the study intervention as randomized.
  - The participant did not meet the study inclusion/exclusion criteria.
  - Major protocol violation – a protocol violation that, in the opinion of the sponsor's study medical monitor, would materially affect assessment of immunogenicity.
  - Blood was taken outside the window (<27 days or >45 days after vaccination).

The clinical question of interest is based on whether the immune response elicited from GBS6 via coadministration with Tdap, without any influence from any other immune-modifying drugs or vaccines, measured in a homogeneous time point, is noninferior to that of GBS6 administered alone (ie, without Tdap). Therefore, all data after intercurrent events, if applicable and collected, will be excluded. Major protocol violations will be determined by clinical review.

- Population-level summary: The GMRs and 2-sided 95% CI estimated by the GMR of IgG concentration measured 1 month after vaccination from the GBS6+Tdap group to the GBS6+placebo group.

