2.1. Study Rationale

GBS6 is being developed to address the global unmet medical need for prevention of infant GBS disease. It is based on the well-established platform of vaccines composed of CPSs conjugated to the CRM₁₉₇ protein that target the polysaccharide capsules of encapsulated bacteria. Maternal immunization with an efficacious GBS vaccine would likely offer benefits beyond existing approaches to prevent infant GBS disease. The vaccine may also protect against adverse fetal outcomes by reducing GBS colonization in pregnant women. Pregnant women may also benefit directly from a GBS vaccine by the prevention of peripartum GBS disease. Other populations, such as adults of advanced age or with particular GBS risk factors, may be considered for GBS6 vaccine evaluation in the future.

Pregnant women are vaccinated globally to prevent neonatal tetanus and pertussis in young infants, and to protect women and their infants against influenza.

Tetanus- and pertussis-containing vaccines are recommended in many countries during pregnancy. In the US, tetanus, diphtheria, and acellular pertussis vaccine (Tdap) is recommended for administration between 27 and 36 weeks' gestation of each pregnancy. As GBS6 is being evaluated for administration within the same timeframe, information on the safety and potential immune interference of Tdap and GBS6 administered concomitantly are important to understand prior to evaluation of GBS6 in late-stage clinical trials and before GBS6 licensure.

Study C1091005 is a descriptive study that will evaluate the concomitant administration of GBS6 and Tdap among nonpregnant women to rule out significant interference. The study is expected to provide data prior to the Phase 3 definitive coadministration assessment program in pregnant women.

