9.1. Estimands and Statistical Hypotheses

9.1.1. Statistical Hypotheses

There are no statistical hypotheses defined in the study.

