9.2. Sample Size Determination

The study sample sizes are not based on any formal statistical hypothesis test considerations. The study aims to have a sufficient number of participants in order to describe the safety and immunogenicity of concomitantly administered Tdap and GBS6. With approximately 100 participants to be enrolled in each group, the lower bound of the 2-sided 95% CI for the IgG GMR, estimated by the GMR of GBS CPS serotype-specific IgG antibodies from the GBS6+Tdap group to the GBS6+placebo group measured 1 month after vaccination, is approximately 0.40, 0.38, 0.53, 0.48, 0.63, and 0.46, assuming that there was no inherent difference between these 2 groups, and the maximum SD (natural logarithm scale) is 3.09, 3.27, 2.15, 2.48, 1.58, and 2.65 for serotypes Ia, Ib, II, III, IV, and V, respectively, from Study C1091001, with a 10% nonevaluable rate.

With a similar assumption of no inherent difference between groups, a similar nonevaluable rate, and 100 enrolled participants in each group, the lower bound of the 2-sided 95% CI for the GMR, estimated by the GMR of anti-pertussis toxin antibodies, anti-FHA antibodies, or anti-PRN antibodies from the GBS6+Tdap group to the placebo+Tdap group measured 1 month after vaccination, is approximately 0.74, 0.78, and 0.72, assuming maximum SDs (natural logarithm scale) of 1.01, 0.85, and 1.12 for anti-pertussis toxin antibody, anti-FHA antibody, anti-PRN antibody endpoints, respectively, and the lower bound of the 2-sided 95% CI for the difference in proportions of participants with anti-tetanus toxoid antibody concentrations ≥ 0.1 IU/mL and participants with anti-diphtheria toxoid antibody concentrations ≥ 0.1 IU/mL measured 1 month after vaccination between the GBS6+Tdap group and the placebo+Tdap group is approximately -0.05 and -0.076, respectively, assuming that the proportions are 0.99 and 0.94 for anti-tetanus toxoid antibody and anti-diphtheria toxoid antibody endpoints from Study B1971015.

The primary safety objective includes the endpoints for local reactions, systemic events, AEs, MAEs, and SAEs.

Table 4 shows the probability of detecting at least 1 event (local reactions, systemic events, AEs, MAEs, or SAEs). The number of participants in each study group is 100, which provides a $>86\%$ chance of observing at least 1 event in a group, assuming a true rate of at least 2%.

Table 4. Probability of Observing at Least 1 Event by Assumed True Event Rates

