## 5. GENERAL METHODOLOGY AND CONVENTIONS

### 5.1. Hypotheses and Decision Rules

There are no statistical hypotheses in the study.

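### SAP 2.2.2 asks whether coadministration is noninferior and the protocol says interference will be ruled out, but the descriptive design has no margin or hypothesis to support either conclusion

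*SAP*

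**What the plan says.** **Purpose.** Protocol 2.1, repeated in the synopsis (1.1): "Study C1091005 is a descriptive study that will evaluate the concomitant administration of GBS6 and Tdap among nonpregnant women to rule out significant interference". The following sentence leaves the definitive coadministration assessment to a Phase 3 program in pregnant women.

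**Clinical question.** SAP 2.2.2 states it three times. For tetanus and diphtheria, and again for the pertussis antigens, the question is whether the Tdap response, "measured in a homogeneous time point, is noninferior to that of Tdap administered alone (ie, without GBS6". For the GBS serotypes it is whether the GBS6 response, "measured in a homogeneous time point, is noninferior to that of GBS6 administered alone (ie, without Tdap".

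**Inference framework.** Protocol 9.1.1: "There are no statistical hypotheses defined in the study". SAP 5.1: "There are no statistical hypotheses in the study". Protocol 9.2: "The study sample sizes are not based on any formal statistical hypothesis test considerations". The primary immunogenicity objectives are to describe responses, and SAP 6.1.2 lists descriptive summary statistics for each of them. Neither document shows a noninferiority margin or a threshold for significant interference.

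**Expected precision.** Protocol 9.2 says the lower 95% limit of the GBS IgG GMR for Ia, Ib, II, III, IV and V "is approximately 0.40, 0.38, 0.53, 0.48, 0.63, and 0.46, assuming that there was no inherent difference between these 2 groups".

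**History.** The protocol's amendment history records that Amendment 2 replaced noninferiority testing with descriptive analysis. The SAP is Version 1, dated 14 Dec 2022 and tied to Amendment 3, and its section 2.1 lists no modifications to the protocol's analysis plan.

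**The concern.** Noninferiority has a meaning only against a margin, and ruling something out requires a stated size to rule out. Here the estimand text and the study purpose use both ideas, while the design provides neither.

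Without a margin fixed in advance, whether a given set of intervals shows noninferiority becomes a judgement made after the data are seen. The results are meant to inform later studies in pregnant women. SAP 7.1 also says interim results may serve future study planning or stopping for early success, and gives no success criterion. A wide GBS interval that is compatible with no effect could then be taken as evidence that interference is absent.

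**Working it through.** **Inputs (Protocol 9.2).** 100 enrolled per group and 10% nonevaluable, so 90 evaluable per group; true GMR = 1; two-sided 95% CI; SDs on the natural-log scale, described as maxima, from Study C1091001. The interval is Student's t on the log scale (Protocol 9.4.2; SAP 5.2.2.3).

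**Step 1. Reproduce the plan's lower limits.** SE = SD × √(2/90) = SD × 0.1491, and lower limit = exp(−t(0.975, 178) × SE), with t = 1.973. For Ia: SE = 3.09 × 0.1491 = 0.461, and exp(−1.973 × 0.461) = 0.403.

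**Step 2. Compare with a two-fold reduction.** The documents give no margin, so 0.5 is an assumption used only for illustration. With true GMR = 1, the chance that the lower limit exceeds 0.5 is Φ(ln 2/SE − 1.96), by normal approximation. For Ia: Φ(0.693/0.461 − 1.96) = Φ(−0.455) = 32%. The observed GMR needed to exclude 0.5 is 0.5 divided by the expected lower limit.

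| Serotype | SD | Limit stated | Limit recomputed | Chance of excluding 0.5 | Observed GMR needed |
|---|---|---|---|---|---|
| Ia | 3.09 | 0.40 | 0.403 | 32% | 1.24 |
| Ib | 3.27 | 0.38 | 0.382 | 30% | 1.31 |
| II | 2.15 | 0.53 | 0.531 | 58% | 0.94 |
| III | 2.48 | 0.48 | 0.482 | 47% | 1.04 |
| IV | 1.58 | 0.63 | 0.628 | 84% | 0.80 |
| V | 2.65 | 0.46 | 0.459 | 42% | 1.09 |

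All six stated limits reproduce. Ia, Ib, III and V fall below 0.5.

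**Step 3. Sensitivity to the benchmark.** Of the six stated limits, none is below 0.33, four are below 0.5 and all six are below 0.67.

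**Step 4. Sensitivity to the SD.** The expected limit equals 0.5 when SD = ln 2/(1.973 × 0.1491) = 2.36. The SD for III would need to be about 5% smaller (2.36/2.48 = 0.95) and that for V about 11% smaller (2.36/2.65 = 0.89). Ia and Ib would need SDs about 24% and 28% smaller (2.36/3.09 = 0.76; 2.36/3.27 = 0.72).

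**Step 5. Tdap endpoints.** The same formula with SDs 1.01, 0.85 and 1.12 gives 0.743, 0.779 and 0.719 for pertussis toxin, FHA and PRN (stated 0.74, 0.78, 0.72). The Miettinen-Nurminen limits at 90 per group are −0.050 for tetanus and −0.076 to −0.078 for diphtheria, depending on rounding of the count (stated −0.05 and −0.076). The limited precision therefore concerns the GBS serotypes, while the missing margin concerns every primary immunogenicity endpoint.

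**The case against.** **The documents already limit the inference.** The objectives, the statistical methods summary and every primary immunogenicity analysis are descriptive, the sentence about ruling out interference itself calls the study descriptive, and no planned output declares noninferiority. Protocol 9.2 prints its expected limits openly. This stands, and it makes the point one of wording and permitted conclusions. It does not remove the conflict: the SAP postdates the move to a descriptive design and still poses a noninferiority question for every primary immunogenicity estimand. Leftover wording from before Amendment 2 is a plausible explanation, but only an inference.

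**A margin could be redacted.** Text is blacked out in the primary row of Protocol 9.4.2 and in SAP 5.3.2. A hidden margin is unlikely, since both documents state that there are no hypotheses.

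**Stronger readings a reader might infer, which the documents do not support:**

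- *That the trial cannot exclude a halving for four serotypes.* The limits are expected values at maximum SDs and a true GMR of 1, each of the four still has a 30% to 47% chance of excluding 0.5, and 0.5 is not a documented threshold.
- *That the noninferiority wording drives the data exclusions.* The exclusion sentence in SAP 2.2.2 does follow it, but the exclusions rest on the hypothetical strategy and on the wish for a response free of other immune-modifying products at a uniform time point. Removing the word would not change which data are excluded.
- *That a favorable conclusion should be barred whenever the CI includes 1.* Noninferiority depends on the lower limit against a margin. With a true GMR of 1, about 95% of 95% intervals include 1, so such a rule would penalize the best case.
- *That the sample size is wrong.* The study was sized for description, and the definitive assessment is planned for Phase 3.

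**Conclusion.** The point holds as a mismatch between the stated question and the design. SAP 2.2.2 and Protocol 1.1 and 2.1 promise an answer on noninferiority, or on interference being ruled out. With no hypothesis and no visible margin or threshold, the design cannot support that answer for any primary immunogenicity endpoint.

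The practical size is greatest for GBS. Under the protocol's own assumptions, the expected intervals leave open reductions of up to about 2.5-fold (Ia), 2.6-fold (Ib), 1.9-fold (II), 2.1-fold (III), 1.6-fold (IV) and 2.2-fold (V), the reciprocals of the recomputed limits. The count of four in six depends on the illustrative two-fold benchmark and on maximum SDs; III in particular lies close to the boundary. The first conclusion, that no margin exists to judge against, depends on neither.

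**What to change.** 1. In SAP 2.2.2, in all three places, replace the noninferiority question with an estimation question: how large is the difference or ratio in immune response between coadministration and single administration?
2. In Protocol 1.1 and 2.1, restate the purpose as estimating the size of any interference.
3. State in the SAP that, because no margin is prespecified, no conclusion of noninferiority or absence of interference will be drawn, and that each result will be interpreted by the largest reduction its CI does not exclude, that is, by the lower confidence limit.

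The cost is wording in the SAP and in the protocol's statement of purpose. No endpoint, analysis, sample size or data collection changes. The stated purpose becomes more modest, in line with what the design can deliver.

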### **2.2.3. Secondary Estimands**

Not applicable.

### **2.2.4. Exploratory Estimands**

The exploratory immunogenicity estimands will use the hypothetical strategy and estimate immune responses induced by GBS6+Tdap, GBS6+placebo, and Tdap+placebo when the intercurrent event would not occur.

## **2.3. Study Design**

### **2.3.1. Overall Design**

This Phase 2, multicenter, placebo-controlled, randomized, observer-blinded study will enroll from US investigative sites approximately 300 healthy nonpregnant women, 18 through 49 years of age, who will be randomized to evaluate concomitant administration of GBS6 and Tdap. Participants will be randomized in a 1:1:1 ratio to receive 20 µg GBS6 and concomitant Tdap, 20 µg GBS6 and placebo, or Tdap and placebo.

Participants will have blood drawn prior to vaccination (Visit 1) and at 1 month after vaccination (Visit 2). E-diaries will be used to collect prompted local reaction and systemic event data for 7 days after vaccination (Days 1 through 7, where Day 1 is the day of vaccination). AEs will be collected through Visit 2. MAEs and SAEs will be collected through Visit 3.

Approximately 300 participants will be randomly assigned to the study interventions to achieve a target of 270 evaluable participants, assuming 10% no evaluability.

Participants will take part in the study from enrollment through approximately 6 months after vaccination.

The end of the study is defined as the date of the last visit of the last participant in the study.

An EDMC will be utilized.

### **3. ENDPOINTS AND BASELINE VARIABLES: DEFINITIONS AND CONVENTIONS**

#### **3.1. Primary Endpoints**

##### **3.1.1. Primary Safety Endpoints**

- Local reactions (pain at the injection site, redness, and swelling) within 7 days after administration of study interventions in each vaccine group.
- Systemic events (fever, fatigue, headache, nausea/vomiting, diarrhea, muscle pain, and joint pain) within 7 days after administration of study interventions in each vaccine group.
- AEs within 1 month after vaccination.
- MAEs and SAEs within 6 months after vaccination.

##### **3.1.1.1. Local Reactions**

During the reactogenicity e-diary reporting period following vaccination (Day 1 through Day 7, where Day 1 is the day of vaccination), participants will be asked to assess redness, swelling, and pain at the injection site and to record the symptoms in the reactogenicity e-diary. Local reactions will be assessed at the injection site on the left arm only.

If a local reaction persists beyond the end of the reactogenicity e-diary period following each vaccination, the participant will be requested to report that information. The investigator will enter this additional information in the CRF.

Redness and swelling will be measured and recorded in measuring device units (range: 1 to 21, and >21) and then categorized during analysis as absent, mild, moderate, or severe based on the grading scale in Table 2. Measuring device units can be converted to centimeters according to the following formula: 1 measuring device unit = 0.5 cm. Pain at the injection site will be assessed by the participant as absent, mild, moderate, or severe according to the grading scale in Table 2. A participant with a severe (Grade 3 or above) local reaction will be prompted to contact the investigator to perform an unscheduled visit and assess the reaction.

